PGD grade 3 has been associated with a 90-day mortality of 16.2% in comparison to a mortality of 9.5% for subjects with PGD Grades 0-1. However, the prognostic significance of PGD extends well beyond the immediate post-operative period. Grade 3 PGD has been associated with a more rapid decline in post-operative pulmonary function and the late development of bronchiolitis obliterans syndrome (BOS). These data suggest that new approaches to reduce PGD are fundamental to improving the morbidity and mortality in lung transplant recipients.

4.3.1 Complex Interaction of Donor and Recipient Risk Factors Contributing to Primary Graft Dysfunction

Using the standardized definition for PGD, numerous donor, recipient, and treatment variables have been identified as potential clinical risk factors for the development of PGD . These reported associations remain limited by the lack of multicenter, prospective, observational studies using consistent procurement techniques. Despite this limitation, both single center and registry reviews have suggested that variables such as donor age , prolonged ischemia time , recipient pulmonary hypertension , recipient diagnosis , and donor requirement for blood transfusion , may all be independent risk factors for PGD.

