#### 5.7.2 Study monitoring

#### 1) Required end points during study drug infusion

• Mean Arterial Pressure:

The recipient's mean arterial pressure (MAP) will be monitored at 1 minute intervals during study drug infusion followed by 15 minute intervals for 1 hour.

• Nitrite and metabolite levels:

Blood samples will be obtained prior to the infusion; at 5, 30, and 60 minutes during the infusion; and at 5, 10, 30, 60, 90, 150 after the infusion to measure plasma and whole blood nitrite, plasma nitrate, red cell iron-nitrosyl-hemoglobin, S-nitroso-hemoglobin and methemoglobin concentrations. However, no sample will be sent for methemoglobin concentration prior to drug infusion. Blood samples will also be obtained every 24 hours for two days for future exploratory biomarker/proteomic studies which would include evaluation of IL6, IL $\beta$ , TNF-a, iNOS and COX-2. Nitrite levels will be measured by established methodologies (ozone-based reductive chemiluminescence) routinely performed in [name] NO Metabolomics Core facility.

2) Required end points post study drug infusion to hospital discharge

Following administration of the Sodium Nitrite, the study subjects will continue to receive usual care for their condition consistent with local transplant treatment protocols. The study will not introduce any modification to the normal care algorithms. Day 0 ( $D_0$ ) will be defined as the day of transplantation and reperfusion. Subsequent study days will be numbered sequentially. The following parameters will be required for collection prospectively. They will be obtained specifically for the study protocol if not requested by the treating physician. If requested by the treating physician the parameters will be recorded from the medical record. Specific parameters required to be monitored following lung transplantation/reperfusion will include:

• Arterial blood gas measurements from D0 to D3

The  $Pa0_2/FiO_2$  ratio and oxygenation index will be calculated based upon an arterial blood gas at D0 (within 6 hours of reperfusion), and D1, D2, and D3. The initial measurement (D0) will be obtained on a FiO2 of 1.0 and PEEP of 5 while on mechanical ventilation. Subsequent measurements will be obtained on the prescribed ventilator settings. Ventilator parameters will be obtained with each blood gas determination. **There will be no arterial blood gas measurement on days patient is extubated.** 

• Chest radiography from D0 to D3

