Plain film portable chest radiography will be obtained on D0 (within 6 hours of reperfusion), and D1, D2, and D3. All chest radiography will be referred to a radiology core for independent review and classification independent of the review required for clinical documentation.

Grade	PaO2/FiO2	Radiograph	
0	>300	Absent	
1	>300	Present	
2	200-300	Present	
3	<200	Present	

The primary end point of PGD will be scored using the following criteria:

The absence of pulmonary infiltrates on plain film radiograph will be assigned Grade 0 independent of the PaO2/FiO2 ratio. All extubated patients will be graded as 0 or 1 based upon the interpretation of the chest radiograph. The need for extracorporeal support and/or inhaled nitric oxide will be documented and automatically assigned a Grade III classification.

The diagnosis of Primary Graft Dysfunction (PGD) requires the exclusion of alternative conditions, which might produce a similar radiographic and physiologic pattern including hyperacute rejection, cardiogenic pulmonary edema, venous anastomotic obstruction, and allograft infection. Exclusion of these conditions will be made by a PGD grading committee composed of transplant physicians not involved in the patient's care at the time of transplant until hospital discharge. Medical records will be reviewed within six to eight weeks of transplantation by the committee to classify PGD.

• Sequential Organ Failure Assessment Score (SOFA):

The SOFA score is a recognized ICU scoring system to define the extent of the patient's organ failure. The scoring system has an individual component score for each of 6 organ systems including **respiratory**, **cardiovascular**, **hepatic**, **coagulation**, **renal** and **neurological** systems . The SOFA Score will be obtained daily at D1, D2, D3, and D4.

- Ventilator Free Days (VFD): Defined as the number of days off mechanical ventilationat 8am through D30 post transplantation.
- ICU Free Days (IFD): Defined as the number of days outside the ICU through D30 post transplantation.
- Hospital Days: Defined as the total number of acute and long term acute (LTAC) hospital days during the index transplant admission.

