- Outcome at 90 days: Patient clinical status at D90 post transplantation including living or deceased, and location. To confirm clinical status of patient on Day 90 post transplant as living or deceased and if living current location, a follow up call with made to the patient or the family n day 90 +/- 7 days.

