## 6 Statistical Consideration

Statistical analysis for the protocol will be primarily exploratory (i.e., hypothesis generating), and no firm conclusion will be drawn based upon a confirmation oriented statistical analysis. The results will be displayed as mean±standard deviation for continuous variables, or frequency (percentage), for discrete variables. For variables with skewed distributions, both nonparametric analysis, and parametric analysis using logarithmically transformed data will be performed. The continuous efficacy variables will be analyzed by analysis of variance (ANOVA) models, which will contain terms of treatment dose, disease type, and treatment-by-disease type interaction. The treatment-by-disease type interaction will be assessed at significance level 0.10. If the treatment-by-disease type interaction is not statistically significant, the interaction effect will be removed from the model. The treatment differences will be assessed by pair-wise comparison between the study population and historical controls, using least-square means from the ANOVA model. If baseline value of each continuous efficacy variable is to be adjusted, data will be analyzed by analysis of covariance (ANCOVA).

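### Ventilator-free and ICU-free days do not require the patient to be alive, hospital days has no rule for death, and the 72-hour oxygenation-index AUC has no rule for patients with only the D0 gas or who die before 72 hours

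*Combined protocol and SAP*

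**What the plan says.** Section 2.4 lists four secondary efficacy endpoints: the oxygenation-index (OI) AUC over the first 72 hours, ventilator-free days, ICU-free days and hospital days. Section 5.7.2 defines the three day counts in one sentence each:

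- VFD: "Defined as the number of days off mechanical ventilationat 8am through D30 post transplantation".
- ICU-free days: "Defined as the number of days outside the ICU through D30 post transplantation".
- Length of stay, which is the third of these counts: "Defined as the total number of acute and long term acute (LTAC) hospital days during the index transplant admission".

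None mentions death. Vital status is a separate item, "Patient clinical status at D90 post transplantation including living or deceased, and location". It is not linked to the counts, and no date of death is named.

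The OI comes from gases on D0, D1, D2 and D3. The D0 gas is taken at FiO2 1.0 and PEEP 5; after that, "Subsequent measurements will be obtained on the prescribed ventilator settings". The same section adds: "There will be no arterial blood gas measurement on days patient is extubated". Its one rule for extubated patients assigns a PGD grade, not an OI value.

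Section 6 plans ANOVA or ANCOVA comparisons with historical controls and states: "For variables with skewed distributions, both nonparametric analysis, and parametric analysis using logarithmically transformed data will be performed". It has no rule for death, for missing values or for constructing the AUC.

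**The concern.** A free-day count is meant to reward survival and recovery together. As worded, VFD and ICU-free days credit every day after death, because a patient who has died is neither ventilated nor in the ICU. An analyst who stops counting at death gets a different score for the same patient, and the plan does not say which is intended.

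Hospital days has a single reading, but fewer days look better and an early death gives fewer days.

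The OI gap does not depend on a death. The sampling rule itself leaves patients extubated before the D1 gas with one value, and one point gives no area. If they are dropped, the best early outcomes leave the comparison with historical controls. If the AUC is taken to the last available gas, a death before 72 hours gives a short and therefore favourable AUC.

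**Working it through.** The plan states no figure for these endpoints, so there is nothing to reproduce. The steps below size the consequences. Assumption: VFD counts D1 to D30.

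**1. VFD for a patient ventilated until death.** Literal score = 30 − last ventilated day. Stopping at death gives 0, since the patient never came off the ventilator.

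| Death after reading on | Literal | Stop at death | Difference in mean of 8 |
|---|---|---|---|
| D2 | 28 | 0 | 28/8 = 3.5 |
| D10 | 20 | 0 | 20/8 = 2.5 |
| D20 | 10 | 0 | 10/8 = 1.25 |

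A survivor ventilated through D10 scores 30 − 10 = 20, so on the literal reading the D2 death ranks better.

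**2. Visibility in the mean.** Take survivors ventilated through D3 (assumed), each scoring 27, and replace one of 8 by a ventilated death. The literal mean moves from 27.0 to:

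- D2: (7×27 + 28)/8 = 27.1
- D10: (7×27 + 20)/8 = 26.1
- D20: (7×27 + 10)/8 = 24.9

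With the death scored 0 it is (7×27)/8 = 23.6 in each case.

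**3. Death after extubation.** A patient extubated before the D2 reading who dies after the D20 reading scores 29 literally, 19 (D2 to D20) if counting stops at death, and 0 if death is scored 0.

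**4. Hospital days.** Counting D0, a D2 death gives 3 days and a D20 death 21. With survivor stay s (assumed), the change in the mean of 8 is (7s + d)/8 − s.

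| s | D2 death (d = 3) | D20 death (d = 21) |
|---|---|---|
| 14 | −1.4 | +0.9 |
| 20 | −2.1 | +0.1 |
| 30 | −3.4 | −1.1 |

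**5. Chance of a death among 8.** Section 3 reports: "PGD grade 3 has been associated with a 90-day mortality of 16.2% in comparison to a mortality of 9.5"% for grades 0-1. The Pittsburgh row of Table 1 gives 55% grade 0-1 (21% + 34%), 20% grade 2 and 25% grade 3. No rate is given for grade 2, so it is taken between the two.

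- Grade 2 at 9.5%: 0.75×9.5 + 0.25×16.2 = 11.2%
- Grade 2 at 16.2%: 0.55×9.5 + 0.45×16.2 = 12.5%
- At least one death by D90, 1 − (1 − m)^8: 61% to 66%
- By D30, if one third to two thirds of those deaths fall by then (assumed): from m = 3.7% to m = 8.3%, giving 26% to 50%
- Before 72 hours, at an assumed m of 0.5% to 2%: 4% to 15%

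**6. OI AUC.** If 1, 2 or 3 of 8 are extubated before the D1 gas (assumed), the AUC rests on 7, 6 or 5 patients. With a trapezoid to the last gas (assumed), OI 12 from D0 to D1 followed by death gives 12 OI-days. A survivor at OI 5 through D3 gives 5×3 = 15, so the death looks better.

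**The case against.** The strongest reply is that these are secondary endpoints in an 8-patient pilot, and Section 6 calls its analysis primarily exploratory and disclaims firm conclusions. Deaths would also be known. Section 10.2 requires record review for adverse events until 72 hours after the last dose, a committee reviews records at six to eight weeks to grade PGD, and status is confirmed at D90. In 8 patients a listing would show any death. This stands as a limit on weight. It does not repair the scores, because knowing of a death does not say how it enters VFD, ICU-free days, hospital days or the AUC. The comparison with historical controls needs one rule for both groups.

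Four stronger inferences are tempting, and the documents do not support them:

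- **That the literal reading hides any death on the ventilator.** It does so only for a very early one; the falls to 26.1 (D10) and 24.9 (D20) are visible.
- **That a 3.5-day shift has a 26-50% chance.** That range covers any death by D30, including later deaths and deaths after extubation. The 3.5-day gap needs a death before 72 hours, at 4-15% under an assumed rate.
- **That the chance of a death by D90 is as high as 76%.** That figure, 1 − (1 − 0.162)^8, needs all eight patients to have grade 3 PGD, against 25% in the Pittsburgh row.
- **That hospital days is ambiguous, or always favours death.** It has one reading, and a late death can lengthen the mean.

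Nor does the gap call for replacing the AUC with a ranking for every patient. A smaller AUC after early extubation points the right way.

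**Conclusion.** The point holds, at moderate weight. Followed literally, the day-count definitions can rank a patient who dies early on the ventilator above a survivor with prolonged ventilation. The choice of reading moves the mean of 8 by 1.25 to 3.5 days for a ventilated death between D20 and D2. Hospital days can make an early death look like benefit. The no-gas rule leaves D0-only patients without a 72-hour AUC, so the fastest recoverers may be lost.

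The day-count sizes rest on counting D1 to D30. The probabilities rest on the quoted 90-day mortality, the Pittsburgh grade mix and an assumed timing of deaths, since the documents give neither D30 nor 72-hour mortality. The donor and recipient exclusions in Sections 7.1.2 and 7.1.4 may lower them. The survivor stays, OI values and numbers extubated early are illustrations. A reader might infer that the trial's main conclusions are at risk, but the safety measures and PGD incidence do not use these scores.

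**What to change.** - **VFD and ICU-free days.** Define them as days alive and off the ventilator, and alive and out of the ICU, through D30. Score death by D30 as 0 and declare this a convention, since it ties a death with a survivor ventilated through D30. Show days alive and free without the zero as a sensitivity check. Do not log-transform scores that can be 0.
- **Date of death.** Add it to the case report form.
- **Hospital days.** Rank in-hospital deaths worst, or report the stay separately for survivors and deaths.
- **OI AUC.** State how it is calculated and keep observed AUCs where they can be computed. Set in advance a rule that keeps D0-only patients in the analysis on the favourable side, for example ranked better than those still ventilated. Rank death before 72 hours worst. Do not carry the D0 value forward, because it is taken at fixed settings and later gases are not.
- **Historical controls.** Apply the same rules where records allow, and list deaths beside these endpoints in both groups.

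The cost is endpoint wording, one data field and a check that the control records hold dates of death and extubation and the D0 to D3 gases, which the documents do not establish. Reported means may be slightly less favourable. Treatment, sampling and sample size do not change.

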## 5.7.3 Optional end points to be obtained from admission to ICU discharge based on standard clinical monitoring

#### (1) Arterial blood gas measurements from D4 to ICU discharge

The Pa02/FiO2 ratio and oxygenation index will be calculated and the worst value for each individual day recorded for analysis. Corresponding ventilator parameters will be recorded.

(2) Plain film portable chest radiography from D4 to ICU discharge

All chest radiography will be referred to a radiology core for independent review and classification independent of the review required for clinical documentation.

(3) Requirement for extracorporeal support and days

Any day beyond  $D_0$  to ICU discharge in which the patient receives extracorporeal support will be counted.

(4) Requirement for inhaled NO support and days

Any day beyond  $D_0$  to ICU discharge in which the patient receives inhaled NO support will be counted.

- Results of Echocardiography -specifically the left ventricular function and estimated pulmonary arterial pressure (PA systolic, PA diastolic, and mean) to evaluate cardiac and pulmonary arterial function.
- D0 to ICU discharge
  - ventilator settings
  - -vital signs
  - 24 hour fluid balance

- hemodynamic indices including MAP, PA pressures, central venous pressures, cardiac index.

- 3) Additional end points to one year post hospital discharge obtained only if needed for patient's standard care
  - Results of pulmonary function tests specifically the FVC, FEV1, and FEV1/FVC ratio.
  - Lung Biopsy Results specifically the diagnosis of acute cellular rejection and grade, bronchiolitis obliterans (BO), and treatment.
  - Complications including major opportunistic infections and subsequent hospitalizations.

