#### 2.4 Endpoints

#### Primary Endpoints Analysis

- The primary endpoint for the safety of Sodium Nitrite administration will be assessed by measurement of methemoglobin levels and mean arterial pressure during the nitrite infusion in the transplant recipient.
- The primary endpoint for the efficacy of Sodium Nitrite infusion will be the incidence of grades 2 and 3 PGD using the International Society for Heart and lung transplant (ISHLT) criteria for PGD based upon the worst value obtained over the initial 72 hours post lung reperfusion (T0-72).

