#### Organ Procurement from the Donor

Consistent with current practice, the initial liter of antegrade flush of the donor lung with Perfadex includes the addition of prostaglandin and nitroglycerin to a 1L bag of the preservation solution. This initial liter of solution WILL NOT include the addition of Sodium Nitrite. Subsequent to this initial liter, any additional preservation solution (Perfadex) will be provided in 2.8 Liter bags only and will include the addition of Sodium Nitrite for injection to achieve a final concentration of 0.69 mg/mL (10 uMolar). Other additives to the preservation solution will include THAM and calcium chloride consistent with local practice. The Sodium Nitrite will be added prior to the infusion of the preservation solution. The actual volume of solution used for both antegrade (PA to PV) and retrograde (PV to PA) flush will be determined by the surgical team directing the procurement and recorded for the purpose of this study. A member of the study team will be present for monitoring of this procedure.

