#### Organ Implantation prior to Reperfusion

At the time of transplant, the first donor lung will be flushed with a cold pneumoplegia solution after the bronchial (1st) anastomosis. The pneumoplegia solution used clinically at UPMC is a 50% Dextrose/autologous blood preparation, which includes Nitroglycerine, Verapamil and Heparin (refer to Appendix C for description of UPMC pneumoplegia solution); and the Sodium Nitrite will be added just prior to use. A second flush of pneumoplegia solution will occur after the PV (3rd, last) anastomosis. The identical pneumoplegia solution as outlined above will be used for the second flush, but at a temperature range of 34- 38 °C. The same process of flushing with pneumoplegia solution will be followed for the second donor lung.

To the recipient at the time of reperfusion:

Sodium Nitrite will be delivered intravenously to the recipient *immediately* prior to the first lung reperfusion as a single infusion of Infuse at 4 mL/min for the first 30 min, followed by 2.2 mL/min for the next 60 min.

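### Inhaled NO and other NO sources are not time-logged across the nitrite infusion and sampling window, and methemoglobin has no pre-infusion sample, so a raised level could not be cleanly attributed to nitrite

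*Combined protocol and SAP*

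**What the plan says.** **Endpoints.** Section 2.4 assesses primary safety by "measurement of methemoglobin levels and mean arterial pressure during the nitrite infusion in the transplant recipient". The metabolism objective in Section 2.3 uses plasma and whole-blood nitrite, nitrate, iron-nitrosyl-hemoglobin, S-nitroso-hemoglobin and methemoglobin.

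**Sampling.** Section 5.7.2 states: "Blood samples will be obtained prior to the infusion; at 5, 30, and 60 minutes during the infusion". Six more draws follow, the last at 150 after the infusion. The same paragraph excludes methemoglobin from the pre-infusion draw. Besides these levels, the only required data during the infusion are MAP readings. D0 "will be defined as the day of transplantation and reperfusion".

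**Inhaled NO.** It appears twice.
- In the PGD scoring rules of Section 5.7.2: "The need for extracorporeal support and/or inhaled nitric oxide will be documented and automatically assigned a Grade III classification".
- In Section 5.7.3, item (4), an optional end point: any day beyond D0 "to ICU discharge in which the patient receives inhaled NO support will be counted".

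Neither entry asks for a dose or for start and stop times.

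**Nitroglycerin.** Section 5.5 places it in two lung-flush solutions. The first litre of donor flush "includes the addition of prostaglandin and nitroglycerin to a 1L bag of the preservation solution". The pneumoplegia is "a 50% Dextrose/autologous blood preparation, which includes Nitroglycerine, Verapamil and Heparin", has study nitrite added to it, and is given twice per lung. The Perfadex volume "will be determined by the surgical team directing the procurement and recorded for the purpose of this study". The available text makes no similar request for pneumoplegia times or volumes.

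**Other agents.** Section 5.6 permits vasoactive drugs during the infusion without naming agents or giving a recording rule. The eligibility criteria in Section 7.1 do not mention nitrates or inhaled NO. Section 6 has no rule for co-exposure.

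**The concern.** The study has eight patients, one arm and no concurrent control. Attributing a blood level to nitrite therefore depends on comparison with the patient's own baseline and on knowing what else was being given. Methemoglobin has neither. The other analytes have a baseline but no exposure log.

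The plan itself foresees inhaled NO after reperfusion, since it makes inhaled NO an automatic Grade III. Yet the only day count starts after the day on which the infusion is given.

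The causality rules lean towards blaming the drug. Under Section 10.3 an event is drug-related if the timing is reasonable and the drug could readily have produced it. Under Section 10.5.2, item 2, an uncertain and questionable relationship is classed as drug-associated for reporting. A high methemoglobin in a patient on inhaled NO would tend to be charged to nitrite. Conversely, a real nitrite effect could be put down to inhaled NO. These results feed the benefit-risk review in Section 10.4 and the case for a larger trial in Section 4.

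**Working it through.** **1. Sampling window.** Inputs: infusion rates (Section 5.5), a 250 mL bag holding 40 mg (Section 5.4), last draw at 150 (Section 5.7.2, minutes assumed).
- Volume: 4 × 30 + 2.2 × 60 = 120 + 132 = 252 mL over 90 minutes, which fits the 250 mL bag.
- Start of infusion to last draw: 90 + 150 = 240 minutes if uninterrupted. The pauses allowed in Section 5.6 lengthen it.

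**2. Window against the day count.** The infusion starts immediately before first-lung reperfusion, so on D0. If it starts by 20:00, an uninterrupted window lies wholly on D0 and item (4) covers none of it. If it starts later, some draws fall on D1, but a day count still cannot place exposure against a draw. A patient given inhaled NO on D0 only would be Grade III with zero inhaled-NO days.

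**3. Draws per analyte.**

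| Analyte | Before | During | After | Total |
|---|---|---|---|---|
| Methemoglobin | 0 | 3 | 6 | 9 |
| Nitrite, nitrate, iron-nitrosyl- and S-nitroso-hemoglobin | 1 | 3 | 6 | 10 |

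For the second row, an exposure already under way is reflected in the pre-infusion value. One that starts or changes later is not separated. For methemoglobin, nothing is separated.

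**4. Flushes.** Each lung is flushed after the bronchial and after the last anastomosis. If the lungs are implanted one after the other, the second lung's flushes can fall after the infusion has begun, bringing nitroglycerin and further nitrite. A stock syringe holds 12 × 0.16 = 1.92 mg nitrite, or 1.92/40 = 4.8% of the recipient infusion. How much nitrite or nitroglycerin reaches the recipient is not stated.

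**5. How much a second source could matter for methemoglobin.** Section 8.1 reports a rise from 0.02% to 5.7% after about 300 mg, and levels not above 3% at about 40 mg. Linear dose scaling (an assumption) gives (5.7 − 0.02) × 40/300 = 0.76 points. The contribution *a* of another source is also assumed. Its share of the total is *a*/(*a* + nitrite effect):

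| Assumed *a* (points) | Nitrite effect 0.76 | Nitrite effect 3 |
|---|---|---|
| 0.5 | 40% | 14% |
| 1 | 57% | 25% |
| 2 | 73% | 40% |

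**6. Late pharmacokinetic draws.** With the 42-minute half-life in Section 8.1 and simple exponential decay (an assumption), the fraction of end-of-infusion nitrite remaining is 0.5^(60/42) = 0.37 at 60 minutes and 0.5^(150/42) = 0.08 at 150 minutes. A source starting after the infusion would weigh most on the late draws, where little study drug is left.

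**7. Patients affected.** The plan gives no inhaled-NO rate. Since inhaled NO implies Grade III here, reported Grade 3 rates give a rough upper guide, if they used the same rule (not stated) and apply to these patients. Over the 10% to 35% range in Section 3, 8 × 0.10 = 0.8 to 8 × 0.35 = 2.8 patients. At the site's own 25%, 8 × 0.25 = 2.

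**The case against.** The case against is substantial, and much of it narrows the point.

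- **D0 inhaled NO is not ignored.** The PGD rule documents the need for it without excluding D0, and the grading committee reviews the medical records at six to eight weeks. Item (4) is an optional support count with the same form as the extracorporeal count in item (3); it was not built as a pharmacokinetic covariate. This stands. What remains is that neither record can be lined up with a draw.
- **High values would be examined.** Section 10.3 names methemoglobinemia as an expected event to be reported within 5 days, and Section 10.5.2 seeks enough information to judge cause. This stands for single events. It does not supply time-aligned exposure for the cohort methemoglobin and metabolite summaries.
- **Most analytes have a baseline.** True, and it protects them against exposures already under way. It does not protect methemoglobin, which has none.
- **Nitroglycerin is the weaker limb.** It is specified only in lung flushes used as standard; no intravenous nitroglycerin to the recipient is specified. Appendix C, which describes the pneumoplegia, was not in the text available to me.
- **The bias is conservative for safety.** If other sources only add methemoglobin, they overstate nitrite toxicity. This stands: only a high value is ambiguous.
- **The analysis is exploratory** under Section 6, with no firm conclusions. That limits the harm, but the safety readout is still the primary objective.

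A reader might infer that inhaled NO on D0 goes unrecorded, or that no level could ever be attributed to nitrite. The documents support neither, for the reasons above.

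**Conclusion.** The point holds as a data-capture gap that should be closed. The plan has no time-aligned record of other NO sources over a window of about 240 minutes that begins on D0, and its primary safety analyte has no pre-infusion value. A raised methemoglobin, or a metabolite rise beginning after the pre-infusion sample, could not be cleanly attributed to nitrite.

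It would be too much to conclude that the safety objective is unanswerable: uniformly low methemoglobin would still support safety whatever else was given.

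The size is uncertain. The 14% to 73% range rests on an assumed 0.5 to 2 points from other sources and, at its upper end, on linear dose scaling. The guide of roughly one to three affected patients rests on borrowed Grade 3 rates. That inhaled NO and nitroglycerin act on these analytes is general pharmacology and is not stated in the documents. None of these figures should be read as an estimate for this trial.

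**What to change.** None of these changes alters clinical care.

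1. In Section 5.7.3, item (4), count inhaled-NO days from D0, so that the count agrees with the PGD rule.
2. In Section 5.7.2, add a time-stamped log through the last pharmacokinetic draw, taken from the existing anesthesia and ICU records. It should hold the dose and start and stop times of inhaled NO and of any intravenous NO donor, and the time of each pneumoplegia flush, because those flushes carry both nitroglycerin and study nitrite.
3. Preferably, send methemoglobin on the pre-infusion draw already planned for the other analytes.
4. In Section 6, report individual methemoglobin and metabolite profiles with co-exposed patients flagged. Any summary that omits inhaled-NO patients should be labelled descriptive: inhaled NO is a post-reperfusion event that itself defines Grade III PGD, so omitting these patients selects on outcome.

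The cost is a few CRF fields from existing charts, one more methemoglobin assay per patient if item 3 is adopted, and flagged listings. The drawback is that the unexposed subset will be smaller than eight and will bear little interpretation on its own.
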